**Measures**

The interview questionnaire is attached.

**Data Collection**

Timeline of Testing: (see diagrams below).

1- Visit 1:

2- Visit 2:

[figure not shown]

Figure 2: Timeline for blood and urine sample collection.

**Eligibility and consent visit**

Participant will only be given appointment after they have been comprehensively assessed for this trial, and will be required to come to Medical Science Precinct/ School of Health Sciences, UTAS. Signed consent will be obtained prior to performing any study related procedures.

Participants will undergo the following procedures:

- i) Anthropometrics: We will measure body weight, height, waist and hip circumference.
- ii) Lifestyle: Potential participants will complete a general health questionnaire (attached) which includes questions regarding family history of T2DM and a physical activity questionnaire (attached). Participants will be provided with a 3-day food record (attached) to complete at home and brought to the next clinic visit (if deemed eligible to continue with the study).
- iii) Blood pressure: Brachial blood pressure will be recorded with a validated Omron HEM 907 device. Measures will be taken with a correct sized cuff, feet flat on floor, back supported and no talking (as per recommendations). After five minutes rest, measures will be taken in duplicate (one minute apart). A second set of duplicate measures (one minute apart) will be taken after 10 minutes rest, and the average of these last two values will be used for analysis. We have recently found that this is the optimal, and most clinically relevant, time to acquire brachial and central BP.

**VISIT 1:****Finger Prick Method**

A finger prick will be performed on the participants to test their blood glucose level using glucometer

Participants will undergo a variety of metabolic and blood pressure measurements. Participants will fast ( $\geq 12$  hours) and refrain from caffeine and alcohol ( $\geq 12$  hours) and refrain from exercise for 48hrs prior to attending the clinic at 8:00-10:00am. T2D participants on metformin will be instructed to discontinue their medication for treating hyperglycaemia on the morning of the study. Testing will be conducted on participants in a quiet, temperate room and in the supine position. A polyethylene catheter will be placed in an antecubital vein for blood sampling. Menstruating females will only be tested in the early follicular phase.

*Clinical Biochemistries*

A blood sample (0.33M EDTA tubes) will be taken to measure clinical chemistries (glucose, insulin, lipids and HbA1c). A second blood sample will be taken, centrifuged at 4°C for 10 minutes, and plasma/serum samples stored at -80°C for analysis of other metabolite, inflammatory markers

*Urine sample*

We will also measure urinary electrolytes (e.g. sodium, potassium, creatinine, albumin), markers of oxidative stress (e.g. 8-Hydroxy-2'-deoxyguanosine) and kidney function. A spot urine sample will be taken at rest and 2hrs following the OGTT.

In addition, spot urine samples will be taken every 4 weeks during the study.

Oral glucose tolerance test (OGTT)

A 2-hour OGTT will be performed to assess glucose tolerance and insulin sensitivity and is a routine clinical test for determining insulin resistance and diabetes. A fasting blood sample (time: -10 minutes) will be taken prior to ingestion of a drink containing 25g of glucose (time: 0 minutes). Blood samples will also be taken at specific time points post-glucose ingestion (0, 30, 60, 90 and 120 minutes), thereby enabling measurement of 2-hour area under the curve (AUC) for glucose and insulin and insulin sensitivity indices.

Whole-body insulin sensitivity will be calculated according to the Matsuda index (17):

Insulin sensitivity =  $10,000 / \sqrt{[(FPG \times FPI) \times (\text{mean OGTT glucose} \times \text{mean OGTT insulin})]}$

Here, FPG represents fasting plasma glucose, FPI- fasting plasma insulin, and mean values the average of 0, 30, 60, 90 and 120-minute plasma concentrations.

Insulin sensitivity of muscle and hepatic tissues will be calculated according to equations validated by Abdul-Ghani et al. (18):

Muscle insulin sensitivity index = (dG/dt) divided by (mean plasma insulin).

Hepatic insulin sensitivity index = glucose AUC0-60 × insulin AUC0-60.

Here, dG/dt refers to the rate of decrease in plasma glucose from peak to nadir (slope of least square fit; excluding any rebound increase in glucose) and AUC0-60 refers to area under the curve during the first 60-minutes of the OGTT.

In addition to these estimates based on dynamic testing, insulin sensitivity derived from fasting steady-state measurements will be calculated by the homeostasis model assessment index (HOMA-IR); that is, fasting plasma insulin × fasting plasma glucose / 22.5

During the OGTT, blood samples will be collected and transferred to ice-cold tubes containing 10µl of 0.33M EDTA, immediately centrifuged at 4°C for 10 minutes and plasma samples stored at -80°C for further analysis.

*Thompson's Super Bioflavonoid Complex® supplementation/ Placebo:*

Participants will be randomly divided into the two study groups. Study group participants (Group-1) will be asked to take 2 capsules of Thompson's Super Bioflavonoid Complex® daily before the meal for 12 weeks (total of 168 capsules per participants). Control group participants (Group-2) will be asked to take placebo capsules for the whole 12 weeks. The Thompson's Super Bioflavonoid Complex®/Placebo capsules will be provided free of charge, for the entire length of the study. However, if participants skip 42 capsules (equivalent to 3 weeks) over the course of the intervention, they will be excluded from the study.

**ARTG Product Link-:** [http://search.tga.gov.au/s/search.html?collection=tga-artg&profile=record&meta\\_i=251014](http://search.tga.gov.au/s/search.html?collection=tga-artg&profile=record&meta_i=251014)

Australian Register of Therapeutic Goods (ARTG) Entry- 251014	
Supplement Facts- Serving Size- 1 Tablet	Amount Per Serving
Thompson's Super Bioflavonoid Complex®	1100 mg
Citrus Bioflavonoid Extract	500 mg

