## METHODS

### Design

**Participants:** Fifty participants recently diagnosed with prediabetes and/or T2DM living in Hobart/Launceston regions will be recruited for this study. The study will be conducted in two clinical areas: 1- Medical Science Precinct, University of Tasmania (UTAS), Hobart. 2- School of Health Sciences, Newnham campus, Launceston. Potential participants will be identified by local media, flyers, local General Practices, as well as by the Diabetes clinic at the Royal Hobart Hospital and Launceston General Hospital. Participants will undergo the following:

1. Medical & lifestyle questionnaires (general health, diet & physical activity questionnaires).
2. Anthropometrics (body weight, height, waist & hip circumference).
3. Blood tests to measure blood glucose, HbA1c, serum lipids, insulin, & oxidative markers (8-hydroxy deoxy Guanosine (8-OHdG), and resistin).
4. DPP-4 activity in the blood before and after 12 weeks.
5. Glucose metabolism (2hr oral glucose tolerance test).
6. Haemodynamic measures (blood pressure, heart rate & ECG).
7. Urinary electrolytes & kidney function.

**Research design:** This is a randomized double-blinded placebo-controlled study. The total duration of the recruitment process is 12 weeks.

Participants will be randomly allocated into two study groups (25 participants in each study group): Study group (Group-1) include participants who use the nutraceutical supplement (Thompson's Super Bioflavonoid Complex®) for 12 weeks and continue on their current anti-diabetic treatment with no interruption. Control group (Group-2) include participants who use the placebo capsules for 12 weeks and continue on their current anti-diabetic treatment with no interruption.

The placebo capsules would contain the same excipients as the active capsules, but the active herbal extract would be replaced by excipients.

The excipients in the Thompson's Super Bioflavonoid Complex are microcrystalline cellulose (BP), calcium hydrogen phosphate dehydrate (USP), silica – colloidal anhydrous (BP), crospovidone (BP) and magnesium stearate (BP).

As per the instruction provided, the supplements will need to be stored below 30 °C in a dry place.

[figure not shown]

Figure 1: Overview of the study.

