### Participants

#### *Inclusion Criteria:-*

For all participants

1. Have been clinically diagnosed with prediabetes and/or early stage type 2 diabetes (on diet and lifestyle intervention or metformin only treatment).
2. Aged between 25 – 75 years.
3. Lean, overweight or obese (BMI 19-35 kg/m^2).
4. Have normal or controlled blood pressure (Seated brachial blood pressure <140/90 mmHg).
5. Have given signed informed consent to participate in the study.
6. Willing to take nutraceutical supplement (Thompson's Super Bioflavonoid Complex®), for 12 weeks.

*Exclusion Criteria:-*

For all participants

1. Age <25 yrs or >75 yrs
2. Morbidly obese with a BMI  $\geq 35$  kg/m^2
3. Not on diet and lifestyle or metformin only treatment for their diabetes (e.g. insulin injections, sulphonylureas, GLP-1 receptor agonists).
4. History of myocardial infarction or stroke
5. History of malignancy within past 5 years (except for non-melanoma skin cancers)
6. Identification of any medical condition requiring immediate therapeutic intervention
7. Uncontrolled hypertension (resting brachial blood pressure  $\geq 160/100$  mmHg)
8. History of severe liver disease
9. History of drug or alcohol abuse
10. Elective major surgery during the course of the study
11. Pregnancy/lactation
12. Currently consuming nutraceutical supplements (especially vitamin C and D)
13. Participation or intention to participate in another clinical research study during the study period.
14. Not willing to take nutraceutical supplements (Thompson's Super Bioflavonoid Complex®), for 12 weeks.
15. Participants with impaired renal function.

Participants will be invited from Hobart/Launceston regions who are able to come to the clinical areas at Medical Science Precinct/School of Health Sciences, UTAS. Venous blood samples & urine samples will be collected at the start of the study. Thompson's Super Bioflavonoid Complex® supplement will be provided to the participants for 12 weeks, and samples will be collected at the end of the study to compare the results of the selected markers aiming to identify the metabolic response to these nutraceutical supplements.

Biomarkers of metabolic response included in this study are 8-hydroxy deoxyguanosine (8-OHdG) (oxidative DNA damage), total lipid peroxidation (lipid peroxidation), interleukin-6 (Inflammatory response) and resistin (adipocytokine response).

*Sample size Justification*

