Our previous data shows that we had statistical significant changes in the levels of 8-OHdG and antioxidants using 40 T2DM patients [16]. Based on these data and assuming 20-25% withdrawal rate from the study, for a two sample test (t-test) with a Type I error of 5% ( $\alpha = 0.05$ ) and 80% power, we will require 50 participants in each group.

*Recruitment*

Potential participants will be identified by radio, flyers, local General Practices, and by the Diabetes clinic at the Royal Hobart Hospital/Launceston General Hospital. Potential participants may be contacted using the National Diabetes Services Scheme (NDSS) through Diabetes Tasmania. Participants from previous studies may be contacted if they have given consent to be contacted for future studies.

Participants who meet the inclusion/exclusion criteria will receive the participant information sheet/consent form inviting them to take part. Contact details of the study coordinator will be given, so that participants can raise any queries or concerns that they have and inform of their interest in participating in the study.

Participants from previous studies will be contacted via telephone, email or mail regarding the study and will be given the opportunity to contact the study coordinator if they are interested. Participants responding to online, print media and radio advertisements will be invited to contact the study coordinator by telephone or email. Initial screening will be based on a health history questionnaire and questions prior to attendance to rule out exclusion criteria.

[figure not shown]

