**VISIT 2 - WEEK 12 TESTING:**

Following the 12 weeks of Thompson's Super Bioflavonoid Complex® supplementation/Placebo, participants will be asked to fast overnight (i.e. not eat food and only drink water on the morning of the study) and stop taking metformin and then at Medical Science Precinct/School of Health Sciences, UTAS. They will undergo an oral glucose tolerance test to measure your glucose tolerance and insulin sensitivity. This will require the participants to drink 25g of glucose (sugar drink) and then the sample of blood will be taken from their vein before and at 0, 30, 60, 90 and 120 min after drinking the glucose solution. Blood pressure and vascular health will also be measured using a blood pressure cuff placed on your upper arm of the participants as well as urine sample will be collected to measure kidney function, electrolytes and oxidative stress. The body composition measurement (height, weight, waist and hip circumference) will also take place.

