### Data analysis

Data analysis will be done using SPSS program (IBM SPSS Statistics version 22), and Microsoft Excel 2010. All values will be expressed as mean  $\pm$  SEM. Statistical analyses will be performed using a one-way ANOVA followed by unpaired Student's t test and paired students t-test (individual results before and after the course of supplements)-LSD- (Least significant difference) (non-parametric, with two-tailed) will be used for non-parametric results (to compare patients versus control results). Results will be considered significant at P equal or < than 0.05.

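### The stated tests compare 8-OHdG without baseline adjustment and cannot use more than two values per person, although baseline is collected and urine is taken every 4 weeks

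*Protocol*

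**What the plan says.** **Sampling.** The *Urine sample* text under Visit 1 lists electrolytes, "markers of oxidative stress (e.g. 8-Hydroxy-2'-deoxyguanosine) and kidney function". It asks for spot urine at rest and 2 hours after the glucose load, and then adds: "In addition, spot urine samples will be taken every 4 weeks during the study". At Visit 2 (week 12), a "urine sample will be collected to measure kidney function, electrolytes and oxidative stress". The general text after the exclusion criteria describes sampling at the start, and says "samples will be collected at the end of the study to compare the results of the selected markers".

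**Specimen.** The numbered list under *Design* puts the same marker in blood: "Blood tests to measure blood glucose, HbA1c, serum lipids, insulin, & oxidative markers (8-hydroxy deoxy Guanosine (8-OHdG), and resistin".

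**Analysis.** *Data analysis* names a one-way ANOVA, followed by an unpaired t-test and a "paired students t-test (individual results before and after the course of supplements". It names no covariate and no repeated-measures method.

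**Role of the marker.** Lower oxidative stress is part of Hypothesis 1. The *Sample size Justification* relies on earlier work in which "we had statistical significant changes in the levels of 8-OHdG and antioxidants using 40 T2DM patients".

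**The concern.** The stated tests do not fit the data collected.

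- With two arms and one value per person, a one-way ANOVA and an unpaired t-test are the same test (F = t²), and both ignore baseline.
- The paired t-test uses baseline, but within a person. It does not compare supplement with placebo.
- If the unpaired t-test were applied to change from baseline, baseline would enter by subtraction. That is less efficient than regression adjustment, and worse than ignoring baseline when the correlation is below 0.5.
- None of these tests accepts the week 4 and week 8 values.

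At stake is precision in a small trial that expects 20-25% withdrawal, on the one marker named individually in the sample-size text.

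**Working it through.** **No planned figure to reproduce.** The sample-size text gives alpha 0.05, 80% power and 20-25% withdrawal, but no difference, SD or correlation. The methods can only be compared under stated assumptions.

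**Inputs**
- 25 per arm, from *Design*. The *Sample size Justification* says 50 per arm; see the last step.
- 20% loss, from the stated 20-25%, so m = 25 × 0.80 = 20 completers per arm.
- Assumed: SD of 1 at every visit, and correlation r = 0.6 between any two values from one person (range 0.3-0.7).
- Assumed: a true week-12 difference of 0.6 SD. Power ≈ Φ(0.6/SE − 1.96).

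**Standard error of the week-12 difference**
1. Unpaired t-test on week 12: √(2/m) = √(2/20) = 0.316.
2. Unpaired t-test on change: √(2 × 2(1 − r)/m) = √(2 × 0.8/20) = 0.283.
3. Baseline-adjusted, no interim urine: √(2(1 − r²)/m) = √(2 × 0.64/20) = 0.253.
4. Repeated-measures model with weeks 4, 8 and 12: generalised least squares with a common baseline mean, and the 20% loss spread equally over the three 4-week intervals. Result: 0.250.

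| Analysis | SE (SD units) | 0.6/SE − 1.96 | Power |
|---|---|---|---|
| Week-12 t-test | 0.316 | −0.06 | 48% |
| Change-score t-test | 0.283 | 0.16 | 56% |
| Baseline-adjusted week 12 | 0.253 | 0.41 | 66% |
| Repeated measures, week 12 | 0.250 | 0.44 | 67% |

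**Where the gain comes from.** Moving from 0.316 or 0.283 to 0.253 needs no interim urine. Adding the interim urine moves 0.253 to 0.250.

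**Sensitivity**
- For r from 0.3 to 0.7, the baseline-adjusted SE runs from √(2 × 0.91/20) = 0.302 to √(2 × 0.51/20) = 0.226. The change-score SE runs from 0.374 to 0.245. The interim urine lowers the adjusted SE by only 0.002-0.003.
- At 25% loss (m = 18.75) and r = 0.6, the four SEs are 0.327, 0.292, 0.261 and 0.257.
- At 50 per arm every SE is divided by √2, so the relative gain is unchanged.

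**Size without reference to n.** Against the week-12 t-test, the adjusted variance is 1 − r² = 0.64 times as large. The t-test would need 1/0.64 = 1.56 times as many completers for the same precision. Against the change score the ratio is (1 + r)/2 = 0.80, or 1/0.80 = 1.25 times as many.

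**The case against.** **The statistical analysis plan may cover this.** It is not shown, and the modelling of repeated secondary data is often left to it. That stands for the interim urine: silence on its use is not an error. It does not dispose of the point, because the protocol is not silent on method. It names its tests, and none adjusts for baseline.

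**Interim results thrown away.** A reader might infer that the week 4 and week 8 8-OHdG results are discarded. No text says so. Nor does any text say that the 4-weekly samples are assayed for 8-OHdG. The shared heading suggests it, but electrolytes or kidney function could be the purpose. The sampling-timeline figure, not shown here, may settle this.

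**Large power gain from repeated urine.** Averaging weeks 4-12 gives an SE of 0.183 and power of about 91% under the same assumptions. That answers a different question and requires the full effect to be present from week 4. The protocol hypothesises an effect of 12 weeks of dosing and compares start with end.

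**Inflated error rates.** Three separate visit tests would give about 12% false positives, and testing both specimens about 9-10%. The protocol proposes neither, so these rates cannot be charged to it.

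**Contradictory specimens.** Blood and urine could both be assayed; the urine text says that it measures these markers in addition. What remains is that nothing says which one is analysed.

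**8-OHdG as sole basis of the sample size.** The text cites 8-OHdG and antioxidants together, and the stated aim is glycaemic control.

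**Conclusion.** The point holds as one about method. The protocol fixes tests that leave the between-arm comparison of 8-OHdG unadjusted for baseline and that cannot use more than two values per person. With 25 per arm, 20% loss and a correlation of 0.6, baseline adjustment raises power for a 0.6 SD effect from about 48% (week-12 t-test) or 56% (change score) to about 66%. The interim urine adds roughly one further point at week 12. The correlation and effect size are assumptions, and the power levels depend on which of the two stated group sizes applies. The ranking of baseline adjustment above both t-tests does not depend on group size and holds across correlations of 0.3-0.7. The blood-or-urine question on its own is a clarification.

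**What to change.** 1. In *Data analysis*, compare the arms on 8-OHdG at week 12 with a baseline-adjusted model that includes all randomised participants with data. Define baseline as the pre-dose fasting sample, since Visit 1 also yields urine after the glucose load and after the first capsule.
2. State which analytes the 4-weekly urine is for. If 8-OHdG is one, fit a single repeated-measures model with arm, visit, arm-by-visit and baseline, and name week 12 as the one contrast. If it is not, say so; the model in item 1 is then sufficient.
3. In *Design* and *Urine sample*, name blood or urine as the analysed 8-OHdG specimen and label the other supportive.

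The cost is a wording change and slightly more analysis work. Extra assay cost arises only if the interim urine is not already due to be assayed for 8-OHdG and the sponsor chooses to add it. The gain at week 12 gives little reason to do so.

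### Excluding participants who skip 42 capsules selects on behaviour after randomisation and can bias the comparison between the arms

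*Protocol*

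**What the plan says.** The Design section describes the trial in these words: "This is a randomized double-blinded placebo-controlled study". It plans "25 participants in each study group". Under Visit 1, in the part on supplementation and placebo, allocation comes first: "Participants will be randomly divided into the two study groups". The active group takes two capsules a day for 12 weeks, a "total of 168 capsules per participants". The same paragraph then states the rule for both groups: "if participants skip 42 capsules (equivalent to 3 weeks) over the course of the intervention, they will be excluded from the study".

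The protocol does not say when the exclusion takes effect. It also does not say whether an excluded participant is still invited to Visit 2, or whether samples already taken are used. Adherence is recorded in a participant logbook; no interim review of it is described.

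Outcome timing matters here. Blood markers, DPP-4 activity and the glucose tolerance test are measured at the start and at week 12. In between, the Visit 1 section plans only spot urine samples every 4 weeks and does not say which analytes are run on them. Separately, the sample size justification is made "assuming 20-25% withdrawal rate from the study".

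**The concern.** Randomisation makes the two groups comparable at the moment of allocation. A rule that later removes people because of how they took their capsules can undo that. People may skip because of poor tolerability or because they notice no benefit, and both can depend on which capsules they received. Those who skip may also differ from the rest in ways that bear on glucose control. If the share removed, or the kind of person removed, differs between arms, the retained groups no longer match, and the observed difference mixes treatment effect with selection.

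This is more than an undefined analysis set, which could be left to a statistical analysis plan. It is a conduct rule that can decide whose week-12 outcomes are collected. A later plan can redefine who is analysed, but it cannot recover glucose tolerance, DPP-4 or blood values that were never taken.

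**Working it through.** **Step 1. The rule's own arithmetic.** Inputs from the Visit 1 section: 2 capsules a day, 12 weeks, threshold 42.
- Total supply: 2 × 7 × 12 = 168, as the protocol states.
- Threshold in time: 42 / (2 × 7) = 3 weeks, as the protocol states.
- Threshold as a share: 42 / 168 = 25%.

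The figures agree with each other. A participant who took 126 of 168 capsules (75%) meets the rule.

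**Step 2. Size of the bias.** Let p be the share excluded in an arm and g the outcome gap, in SD units, between retained and excluded participants of that arm. The full-arm mean is (1 − p) × retained mean + p × excluded mean, so the retained mean differs from it by p × g. With the same g in both arms:

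bias = (p_active − p_placebo) × g

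The protocol gives neither p nor g. Both scenarios are assumptions:
- Mild: 20% v 10%, g = 0.5 SD. Bias = 0.10 × 0.5 = 0.05 SD.
- Strong: 25% v 5%, g = 1 SD. Bias = 0.20 × 1 = 0.20 SD.

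With equal shares and equal gaps the bias is zero.

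**Step 3. Effect on the false-positive rate.** Two-sided two-sample t-test at 5%, no true effect, 20 per arm. Here 20 is the planned 25 less 20%, taken as a round working figure. Degrees of freedom are 38, the critical value is 2.024, and the noncentrality is bias × √(20/2).
- Bias 0.05 SD: 0.05 × 3.162 = 0.158; rejection probability 5.3%.
- Bias 0.20 SD: 0.20 × 3.162 = 0.632; rejection probability 9.5%.

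**Step 4. Does keeping non-adherers raise power?** The protocol states no effect size, so d = 0.8 is an assumption. Two-sided t-test at 5%:

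| Scenario | n per arm | d | Power |
|---|---|---|---|
| Adherers only, 20% removed | 20 | 0.80 | 69% |
| All kept, 20% non-adherers keep half the effect | 25 | 0.8 × (0.8 + 0.2 × 0.5) = 0.72 | 70% |
| All kept, 20% non-adherers keep none of it | 25 | 0.8 × 0.8 = 0.64 | 60% |

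Analysing everyone therefore gives about 60% to 70%, against 69% with adherers only. Power is roughly unchanged or lower.

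**The case against.** The strongest reply is that the text does not establish how much is lost. The threshold applies over the whole intervention and adherence is kept in a logbook, so it may first be recognised at the week-12 visit, when outcomes could still be taken. The study is double-blind and the rule is the same for both groups, which limits differential skipping from knowing the allocation. The protocol gives no sign that adherence will differ by arm, and the mild scenario leaves the false-positive rate almost at its nominal level. Analysis sets may be defined in a plan not shown here.

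Much of this stands. A reader might infer four stronger things that the document does not support:
- **That excluded participants never give a Visit 2 value.** The protocol does not say when exclusion happens, so this holds only for those removed before week 12.
- **That no post-treatment data exist for them.** The 4-weekly spot urine samples may exist, and urine is where the protocol measures 8-OHdG.
- **That the rule produces part of the 20–25% loss.** The sample size text speaks only of withdrawal and does not say whether adherence exclusions count within it.
- **That keeping non-adherers restores power from 69% with 20 per arm to the 79% of 25 per arm at d = 0.8.** That comparison credits the change with recovering every withdrawal and ignores dilution; step 4 shows no dependable gain.

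What the reply does not remove is the rule itself. Blinding does not prevent skipping caused by tolerability or perceived lack of effect. A withdrawal allowance covers lost numbers but not selection. A participant first identified at week 12 is still, on the wording, out of the study.

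**Conclusion.** The concern holds in this form: the protocol fixes an adherence-based exclusion after randomisation. Read literally, it restricts the blood, DPP-4 and glucose tolerance comparison to adherers, and the result may be biased.

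The size is unknown. Under the assumed scenarios, the bias runs from 0.05 to 0.20 SD and the false-positive rate from 5.3% to 9.5% with 20 per arm. These figures rest on assumed exclusion shares and gaps, a common gap in both arms, and equal arm sizes; the direction cannot be told in advance. The case rests on bias, not on power or sample size.

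This should be fixed. The documents give no likelihood that the threshold will be met and no evidence of a difference between arms, so they do not show that the trial's result is invalid.

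**What to change.** Replace the exclusion sentence with wording such as: *Participants who miss capsules remain in follow-up, are invited to Visit 2, and are analysed in the group to which they were randomised. Those who miss 42 or more capsules are left out only of a supportive per-protocol analysis.* This concerns follow-up and analysis only; it says nothing on whether capsules are continued.

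The cost is a one-sentence amendment and the effort of bringing non-adherers back. Visit 2 is already scheduled for all participants. The statistical downside is some dilution of the effect in the main analysis, so no power gain should be claimed for the change. The amendment needs to be in place before anyone is removed, because week-12 values not taken cannot be obtained afterwards.
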